7.2 Discussion of Study Design, Including Choice of Control Group

The primary objective of this study is to evaluate the effect of KRN23 therapy on improving rickets in children with XLH compared with an active control (oral phosphate/active vitamin D therapy). Secondary efficacy objectives are to evaluate the effect of KRN23 compared with active control on growth velocity, lower extremity deformity (ie, bowing), changes in serum phosphorus and other PD markers, walking ability and patient-/parent-reported pain, fatigue, and physical function/mobility. Dental outcomes will be evaluated as an exploratory objective. The safety objective will be to establish the safety and tolerability profile of KRN23 in the treatment of pediatric patients with XLH, including AEs (eg, nephrocalcinosis), as compared with active control, and immunogenicity profile.

An open-label study design was chosen since blinding such a study would be problematic due to the different methods of administration and the individualized nature and frequent dose adjustments needed with oral phosphate/active vitamin D therapy.

Data from the ongoing pediatric Phase 2 study (UX023-CL201) helped establish the dose regimen and provided information for the design of this Phase 3 clinical trial in children with XLH. Interim data from the pediatric Phase 2 study suggested KRN23, administered Q2W at approximately 0.8 mg/kg for 40 weeks, increased serum phosphorus by an average of 0.7 mg/dL; increases of > 0.5 mg/dL were seen in 83.3% of subjects. Serum 1,25(OH)₂D concentrations and TmP/GFR levels also increased, demonstrating overall improved phosphorus homeostasis. The increases in serum phosphorus and 1,25(OH)₂D were sufficient to provide substantial healing of rickets. No subjects have experienced serum phosphorus levels above the upper limit of normal. The Q2W dosing regimen was chosen for this Phase 3 study because it appeared to produce a more stable and consistent increase in serum phosphorus levels with less fluctuation over time than the Q4W dosing regimen, and a safety profile that was not substantially different from the Q4W dosing regimen.

Although there are no approved therapies for children with XLH, the most common treatment consists of multiple daily doses of oral phosphate combined with appropriate doses of active vitamin D analogs, most frequently calcitriol or alfacalcidol. Because of the variability in the doses and dosing frequencies of oral phosphates and active vitamin D therapies in clinical practice, these treatments will be individualized for each subject at the investigator's discretion, but general guidance is provided based on expert recommendations in the US and Europe as described in [Table 7.1.1](#) and [Table 7.1.2](#).

The duration of treatment is intended to define whether KRN23 is safe for long-term use and provide sufficient insight on sustained clinical effects and improvements in rickets and active bone disease in pediatric XLH patients. The primary analysis will be at Week 40; analyses at Week 64/EOS I and Week 140/EOS II will assess the durability of treatment effect, additional efficacy outcomes, and long-term safety.

Change in rickets as measured by the RGI-C is deemed to be an appropriate primary efficacy endpoint in this study since it is the basis for, and correlates with the major morbidities patients with XLH suffer during their lifespan. A disease-specific RGI-C scale can be used to evaluate treatment-related changes in the severity of rickets and bowing in an individual subject. The RGI-C system of evaluating pre- and post- images in a side-by-side comparison is also ideal for the evaluation of healing of rickets as it most closely resembles the approach used by radiologists in the clinical setting to evaluate changes in the appearance of bone. Three pediatric radiologists not affiliated with the conduct of the study and who are blinded to subject number and treatment assignment will be contracted by a central imaging facility to perform RGI-C ratings. The ratings will be performed independently using an EDC system with the raters having no opportunity to discuss images or compare ratings. The mean of the scores assigned by the 3 independent raters is used to calculate an RGI-C wrist score, an RGI-C knee score, and a global RGI-C score.

The primary hypothesis of the primary endpoint is to test whether there is a difference between the KRN23 and active control (oral phosphate/active vitamin D) groups in the mean RGI-C global scores at Week 40. The RSS will serve as a complementary analysis to the RGI-C scale and is the method currently being used in the ongoing pediatric Phase 2 Study.

Additional secondary endpoints are designed to evaluate the beneficial impact of KRN23 in maximizing growth, restoring phosphorus homeostasis, ameliorating defective bone mineralization, reducing the clinical burden of disease, as well as to evaluate the safety of KRN23 in pediatric XLH.

The purpose of Treatment Extension Period is to continue to provide KRN23 treatment after the Treatment Period to subjects in Europe, the US, Canada, and Australia while also continuing to collect long-term safety and efficacy data.

7.3 Selection of Study Population

The proposed patient population for this Phase 3 study is pediatric patients with a diagnosis of XLH and rickets (as documented by bilateral PA hand/wrist radiographs). The proposed key inclusion/exclusion criteria are summarized in Sections 7.3.1 and 7.3.2.

To ensure that appropriate patients are selected, eligibility requirements include demonstrated hypophosphatemia, radiographic evidence of rickets, and genetic evidence consistent with a diagnosis of XLH. *PHEX* sequence variants will be classified consistent with the joint consensus recommendations of the American College of Medical Genetics and Genomics and the Association for Molecular Pathology (Richards et al. 2015). Patients with *PHEX* mutations classified as pathogenic, likely pathogenic, and possibly pathogenic will be included. Patients with *PHEX* variants of uncertain significance will also be included, as was recommended by experts in pediatric XLH. There are hundreds of variants of the *PHEX* gene and many of these have not yet been fully characterized. The study also requires patients to receive oral phosphate/active vitamin D therapy for ≥ 12 consecutive months prior to screening (for children ≥ 3 years of age) or ≥ 6 consecutive months (for children < 3 years of age), 7 days prior to the Randomization Visit..

To ensure that the patients enrolled will have open epiphyses for the duration of the study, only patients ≤ 12 years of age will be included and patients with a Tanner stage 4 or higher will be excluded. Limiting the maximum age to 12 years will help to ensure patients' epiphyses will remain open during the course of the study so that changes in rickets and growth can be evaluated. Week 40 results (N=36) from Phase 2 Study (UX023-CL201) indicated that to best demonstrate a treatment effect and maximize the ability to detect change, baseline rickets should be clearly evident radiographically; the minimal threshold of baseline rickets severity to consistently detect change with treatment based on the current UX023-CL201 data is an RSS score of ≥ 1.5 . To ensure that all patients will have significant rickets at baseline, the study will include patients with a baseline total RSS of 2.0 or higher. Patients will be required to have been on oral phosphate/active vitamin D treatment for at least 12 consecutive months (for children ≥ 3 years of age) or ≥ 6 consecutive months (for

children <3 years of age) and have residual disease despite this in order to show the effect of KRN23 in a relevant population in which the unmet medical need is very clear. A majority of patients with XLH receive treatment within the first 2 years of life. Therefore, the study will not enroll any treatment-naïve patients. To ensure the protection and safety of the study population, the study excludes patients with evidence of hyperparathyroidism, hypocalcemia, and hypercalcemia.

Females are affected more frequently than males, consistent with X-linked dominant inheritance (Ichikawa et al. 2013). However, it is unclear whether the severity of disease is affected by sex or gene dosage. Therefore, no more than 70% female subjects will be enrolled.

Children with XLH undergo a normal pubertal growth spurt. Post-pubertal height is predicted by pre-pubertal height, indicating that loss of height potential generally occurs prior to puberty. Published retrospective data suggest that earlier treatment leads to better outcomes for children with XLH (Makitie et al. 2003), (Quinlan et al. 2012). Thus, initiation of therapy at early ages is recommended to achieve improved height outcomes (Carpenter et al. 2011). Consequently, children younger than 5 years of age were included to determine if earlier treatment with KRN23 would confer greater benefits in improving rickets and growth potential, as well as in restoring normal phosphorus homeostasis. At least 20 subjects aged 1 to < 5 years will be included (approximately 10 in each treatment arm).

The Sponsor has taken reasonable measures to ensure the protection and safety of this population. Patients with evidence of tertiary hyperparathyroidism or nephrocalcinosis will be excluded. Appropriate pediatric expertise will be available at all trial sites, and site personnel will be focused on minimizing risk, fear, pain and distress during conduct of the study.

7.3.1 Inclusion Criteria

Note: All laboratory evaluations required for study eligibility will be determined centrally

Individuals eligible to participate in this study must meet all of the following criteria:

- 1) Male or female, aged 1 to ≤ 12 years with radiographic evidence of rickets with a minimum rickets severity score (RSS) total score of 2.0 as determined by central read
- 2) *PHEX* mutation or variant of uncertain significance in either the patient or in a directly related family member with appropriate X-linked inheritance
- 3) Biochemical findings associated with XLH: Serum phosphorus < 3.0 mg/dL (< 0.97 mmol/L)*
- 4) Serum creatinine below the age-adjusted upper limit of normal *
- 5) Serum 25(OH)D above the lower limit of normal (≥ 16 ng/mL) at the Screening Visit**

- 6) Have received both oral phosphate and active vitamin D therapy for ≥ 12 consecutive months (for children ≥ 3 years of age) or ≥ 6 consecutive months (for children <3 years of age) 7 days prior to the Randomization Visit
- 7) Willing to provide access to prior medical records for the collection of historical growth and radiographic data and disease history.
- 8) Provide written or verbal assent (as appropriate for the subject and region) and written informed consent by a legally authorized representative after the nature of the study has been explained, and prior to any research-related procedures.
- 9) Must, in the opinion of the investigator, be willing and able to complete all aspects of the study, adhere to the study visit schedule and comply with the assessments.
- 10) Females who have reached menarche must have a negative pregnancy test at Screening and undergo additional pregnancy testing during the study. Female subjects of childbearing potential must be willing to use a highly effective method of contraception for the duration of the study plus 12 weeks after stopping the study drug. Sexually active male subjects with female partners of childbearing potential must consent to use a condom with spermicide or a highly effective method of contraception for the duration of the study plus 12 weeks after stopping the study drug.

7.3.2 Exclusion Criteria

Individuals who meet any of the following exclusion criteria will not be eligible to participate in the study:

- 1) Tanner stage 4 or higher in any of the following: genitals, breast, or pubic hair, based on physical examination
- 2) Height percentile $> 50^{\text{th}}$ based on country-specific norms
- 3) Use of aluminum hydroxide antacids (eg, Maalox[®] and Mylanta[®]), systemic corticosteroids, acetazolamide, and thiazides within 7 days prior to the Screening Visit
- 4) Current or prior use of leuprorelin (eg, Lupron[®], Viadur[®], Eligard[®]), triptorelin (TRELSTAR[®]), goserelin (Zoladex[®]), or other drugs known to delay puberty
- 5) Use of growth hormone therapy within 12 months before the Screening Visit
- 6) Presence of nephrocalcinosis on renal ultrasound grade 4 based on the following scale:
 - 0 = Normal
 - 1 = Faint hyperechogenic rim around the medullary pyramids
 - 2 = More intense echogenic rim with echoes faintly filling the entire pyramid
 - 3 = Uniformly intense echoes throughout the pyramid
 - 4 = Stone formation: solitary focus of echoes at the tip of the pyramid

- 7) Planned orthopedic surgery, including osteotomy or implantation or removal of staples, 8-plates, or any other hardware, within the first 40 weeks of the study
- 8) Hypocalcemia or hypercalcemia, defined as serum calcium levels outside the age-adjusted normal limits*
- 9) Evidence of hyperparathyroidism (PTH levels 2.5X upper limit of normal [ULN])
- 10) Use of medication to suppress PTH (eg, cinacalcet, calcimimetics) within 2 months prior to the Screening Visit
- 11) Presence or history of any condition that, in the view of the investigator, places the subject at high risk of poor treatment compliance or of not completing the study.
- 12) Presence of a concurrent disease or condition that would interfere with study participation or affect safety
- 13) History of recurrent infection or predisposition to infection, or of known immunodeficiency
- 14) Use of a therapeutic monoclonal antibody within 90 days prior to the Screening Visit or history of allergic or anaphylactic reactions to any monoclonal antibody
- 15) Presence or history of any hypersensitivity to KRN23 excipients that, in the judgment of the investigator, places the subject at increased risk for adverse effects.
- 16) Use of any investigational product or investigational medical device within 30 days prior to screening, or requirement for any investigational agent prior to completion of all scheduled study assessments.

OR, in Japan, use of any investigational product or investigational medical device within 4 months prior to screening, or requirement for any investigational agent prior to completion of all scheduled study assessments.

* Criteria to be determined based on overnight fasting (min. 4 hours) values collected at the Screening and/or Baseline Visit

** If 25(OH)D levels are below the normal range, 25(OH)D supplementation will be prescribed. Assuming a subject meets all other eligibility requirements, the subject may be rescreened after a minimum of 7 days of treatment

7.3.3 Removal of Subjects from Therapy or Assessment

In accordance with the Declaration of Helsinki, subjects have the right to withdraw from the study at any time for any reason. The investigator and Ultragenyx also have the right to remove subjects from the study. Ultragenyx must be notified of all subject withdrawals as soon as possible. Ultragenyx also reserves the right to discontinue the study at any time for either clinical or administrative reasons and to discontinue participation of an individual subject or investigator due to poor enrollment or noncompliance, as applicable.

Subjects may be removed from the study for the following reasons:

- Occurrence of an unacceptable AE
- An illness that, in the judgment of the investigator or Ultragenyx, might place the subject at risk or invalidate the study
- Pregnancy in subject
- At the request of the subject, investigator, or Ultragenyx, for administrative or other reasons
- Protocol deviation or noncompliance

If the reason for removal of a subject from the study is an AE, the AE and any related test or procedure results will be recorded in the source documents and transcribed onto the Case Report Form (CRF). Each clinically significant abnormal laboratory value or other clinically meaningful abnormality should be followed until the abnormality resolves or until a decision is made that it is not likely to resolve. If such abnormalities do not return to normal within 12 weeks after the last dose given, their etiology should be identified and Ultragenyx should be notified. All unscheduled tests must be reported to Ultragenyx immediately.

If a subject discontinues from the study prematurely, every reasonable effort should be made to perform the Early Termination Visit procedures within 4 weeks of discontinuation. Subjects who discontinue KRN23 due to an SAE will be monitored for safety for a period of 12 weeks after the date of last study drug administration.

7.3.3.1 Stopping Rules

A Data Monitoring Committee (DMC) will be constituted for Study UX023-CL301 and will act in an advisory capacity to monitor the safety of KRN23 on a routine basis throughout the trial (Section 7.6.6). The DMC may provide advice to Ultragenyx to aid in the determination of whether study enrollment should be paused or if the study should be stopped. If the Sponsor deems it appropriate to restart the trial following an internal safety review, this will be done only following approval by Regulatory Authorities.

Individual subjects who experience any unexpected and possibly, probably, or definitely drug-related SAEs (Section 8.5.3) that represent a change in the nature or an increase in frequency of the serious event from their prior medical history will be assessed as to whether the subject will continue on the study.

Individual subjects will be monitored for renal ultrasound (Section 7.5.3). If new or clinically significant worsening in mineralization is considered clinically meaningful by the investigator and/or sponsor and related to study drug, the subject will be discontinued from the study.

Regulatory Authorities, as well as the Institutional Review Board (IRB)/Ethics Committee (EC) will be informed should unexpected and possibly, probably, or definitely drug-related

SAEs occur. A full clinical evaluation of the event will be performed in order to make a decision regarding what actions to take, including whether to recommend stopping the study. Regulatory Authorities, as well as IRBs/ECs, will be informed if the study is paused or stopped.

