SV	Screening Visit
TmP/GFR	ratio of renal tubular maximum reabsorption rate of phosphate to glomerular filtration rate
TRP	tubular reabsorption of phosphate
ULN	upper limit of normal
US	United States
WBC	white blood cell
XLH	X-linked hypophosphatemia

Definition of Terms

Investigational Product is defined as, “A pharmaceutical form of an active ingredient or placebo being tested or used as a reference in a clinical trial, including a product with a marketing authorization when used or assembled (formulated or packaged) in a way different from the approved form, or when used for an unapproved indication, or when used to gain further information about an approved use” (from International Conference on Harmonisation of Technical Requirements for Registration of Pharmaceuticals for Human Use [ICH] Harmonised Tripartite Guideline E6: Guideline for Good Clinical Practice). The terms “Investigational Product” and “study drug” are used interchangeably in the protocol and refer to KRN23.

The terms “Active Control” or “Active Control Arm” refer to oral phosphate/active vitamin D therapy.

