6 STUDY OBJECTIVES

Primary Objective:

- Evaluate the effect of KRN23 therapy in improving rickets in children with XLH compared with the active control (oral phosphate/active vitamin D)

Secondary Efficacy Objectives:

Evaluate the effects of KRN23 as compared with the active control on:

- Growth velocity and lower extremity deformity
- Pharmacodynamic markers that reflect the status of phosphorus homeostasis, including serum 1,25(OH)₂D, serum and urinary phosphorus, ratio of renal tubular maximum reabsorption rate of phosphate to glomerular filtration rate (TmP/GFR), and tubular reabsorption of phosphate (TRP)
- Biochemical markers of bone turnover that reflect rickets severity (alkaline phosphatase [ALP])
- Walking ability and patient-/parent-reported pain, fatigue, and physical function/mobility

Pharmacokinetic Objective:

Assess the PK of KRN23 throughout the dosing cycle

Safety Objective:

Evaluate the safety and tolerability profile of KRN23 in the treatment of children with XLH (aged 1 to ≤ 12 years), including adverse events (AEs) (eg, nephrocalcinosis), as compared with active control, and immunogenicity profile

Treatment Extension Period Objective:

To evaluate the long-term safety and efficacy of KRN23

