7.5.3.12 Dose-limiting Toxicity

A DLT is defined as the occurrence of any of the following:

- Unexpected SAEs occurring during treatment considered to be either definitely, probably, or possibly related to the investigational product or the active control
- A confirmed serum phosphorus level of ≥ 6.5 mg/dL (defined as hyperphosphatemia) at any time after dosing

If a subject experiences a DLT, the planned dosing for that subject will be evaluated by the Investigator and Medical Monitor. The outcome of this investigation will determine the subjects' continuation or withdrawal from the study.

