8.5.3 Relationship of Adverse Events to Study Drug

The investigator will assess the potential relationship of the AE to study drug using the following descriptions. During the Treatment Period, the relationship of the AE to KRN23 will be assessed for subjects in the KRN23 arm, and the relationship of the AE to oral phosphate and to active vitamin D will be assessed for subjects in the active control arm. During the Treatment Extension Period, the relationship of the AE to KRN23 will be assessed.

Categories of attributions for “Unrelated” events:

- **Unrelated:** This category applies to an AE that *is clearly not related* to the investigational agent/procedure.
- **Unlikely Related:** This category applied to an AE that *is doubtfully related* to the investigational agent/procedure.

Categories of attributions for “Related” events:

- **Possibly Related:** This category applies to an AE that *may be related* to the investigational agent/procedure.
- **Probably Related:** This category applies to an AE that *is likely related* to the investigational agent/procedure.
- **Definitely Related:** This category applies to an AE that *is clearly related* to the investigational agent/procedure.

For the purposes of reporting to regulatory agencies, AEs deemed as Definitely, Probably or Possibly Related will be considered Related and those deemed Unrelated or Unlikely Related will be considered Unrelated.

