8.8.7 Renal Ultrasound

Renal ultrasound will be conducted with findings of nephrocalcinosis graded on a 5-point scale by a central reader. These results will be summarized by time point and presented by treatment group. Furthermore, a grade shift table summarizing changes from baseline by time point will also be created.

A listing of renal ultrasound/nephrocalcinosis scores will also be provided.

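### By the protocol's definition of study drug, removal for renal mineralization is mandatory for KRN23 and only discretionary for control, so later-visit ultrasound summaries can favour KRN23 at equal risk

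*Protocol*

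**What the plan says.** - **The rule.** Protocol 7.3.3.1 has each subject monitored by renal ultrasound. If new or worsening mineralization is considered "clinically meaningful by the investigator and/or sponsor and related to study drug, the subject will be discontinued from the study". The consequence is exit from the study, not only from treatment.
- **The definition.** Protocol Section 4 states that the terms investigational product and study drug "are used interchangeably in the protocol and refer to KRN23". The active control terms are defined separately and "refer to oral phosphate/active vitamin D therapy".
- **A neighbouring rule.** Protocol 7.5.3.12 counts unexpected serious events that are "either definitely, probably, or possibly related to the investigational product or the active control". SAP 5.16 repeats that rule but leaves out the active control.
- **Looser usage.** Protocol 8.5.3 is titled for relationship to study drug, yet it says that in the Treatment Period "the relationship of the AE to oral phosphate and to active vitamin D will be assessed for subjects in the active control arm".
- **Discretionary removal.** Protocol 7.3.3 allows, without requiring, removal of any subject for an unacceptable adverse event.
- **The comparison at stake.** The safety objective in Protocol Section 6 covers the profile of KRN23 "including adverse events (AEs) (eg, nephrocalcinosis), as compared with active control, and immunogenicity profile".
- **The planned analysis.** SAP 8.8.7 summarizes nephrocalcinosis grade by time point and arm, and adds that "a grade shift table summarizing changes from baseline by time point will also be created". It names no worst post-baseline grade.

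**The concern.** Taken by its own definition, the mandatory rule cannot be triggered by oral phosphate or active vitamin D. A KRN23 child with a related finding at Week 24 must leave, while a control child with the same finding may stay and be scanned at Weeks 40 and 64. The children who leave are those who have worsened, so the KRN23 arm's later-visit data would be incomplete for a reason tied to the outcome.

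The trigger is also open to knowledge of the arm. The grade comes from a blinded central reader (Protocol 7.5.3.6), but clinical meaning and relatedness are judged by the investigator and/or sponsor in an open-label trial. Because the definition and the usage differ, two sites could apply the rule differently.

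At stake is how the later-visit renal ultrasound comparison reads. To a lesser degree, so are the Week 40 and Week 64 radiographs of the same children.

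**Working it through.** The documents give no nephrocalcinosis rate, so there is no plan figure to reproduce. The only trial number used is 30 children per arm (Protocol 7.6.1).

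**1. Which arm the rule covers.** Section 4 ties study drug to KRN23 and gives the control its own term. Section 7.5.3.12 shows the protocol naming the control when it means both arms. Section 7.3.3.1 does not name it. Section 8.5.3 points the other way. By the definition, removal is mandatory for KRN23 and discretionary for control (7.3.3). By the usage in 8.5.3, it would be mandatory in both.

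**2. What remains of a child removed after the Week 24 scan.**
- The Week 24 scan is already recorded.
- An Early Termination ultrasound is due (Protocol 7.5.3.6; Table 2.3, footnote 27), with the visit to take place within 4 weeks of discontinuation.
- The adverse event is tabulated by arm, both as an event to monitor and as an event leading to study discontinuation (SAP 8.8.1). Nephrocalcinosis is a listed term (SAP Appendix 10).
- SAP 7.2.3 puts all data points into safety shift tables. For by-visit summaries, however, a safety scan 14 days or more from the nearest scheduled visit is not mapped, and a scan nearer to Week 24 gives way to the scheduled one. An Early Termination scan between Weeks 24 and 28 therefore does not fill Week 40 or Week 64.
- Tables 2.2 and 2.3 mark no ultrasound at the later safety follow-up visit.

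**3. Effect on the Week 64 proportion.** Let n = 30 per arm, w = children who worsen in each arm (equal true risk) and r = worsened KRN23 children removed. Assume no reversal and no control child removed.

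KRN23 observed = (w − r)/(n − r); control observed = w/n; gap = w/n − (w − r)/(n − r) = r(n − w)/[n(n − r)]. The gap is positive whenever r > 0 and w < n.

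| w | r | KRN23, Week 64 | Control, Week 64 | Gap (points) |
|---|---|---|---|---|
| 3 | 1 | 2/29 = 6.9% | 3/30 = 10.0% | 3.1 |
| 3 | 3 | 0/27 = 0% | 3/30 = 10.0% | 10.0 |
| 6 | 3 | 3/27 = 11.1% | 6/30 = 20.0% | 8.9 |
| 6 | 6 | 0/24 = 0% | 6/30 = 20.0% | 20.0 |
| 9 | 4 | 5/26 = 19.2% | 9/30 = 30.0% | 10.8 |
| 9 | 9 | 0/21 = 0% | 9/30 = 30.0% | 30.0 |

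Counted as any post-baseline worsening, both arms stay at w/30 in every row. If control children were removed in equal number, the gap would vanish: with w = 3 and one removed per arm, both arms read 2/29.

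**4. Radiographs.** A child who leaves after Week 24 has no post-baseline film, so Protocol 7.5.1 and 7.5.2.1 lead to an Early Termination film at about Week 28. SAP 7.2.3 sends such a film to the closest scheduled visit. Its 14-day limit applies only to pharmacodynamic, pharmacokinetic and safety data. The post-baseline X-ray visits in the Treatment Period are Weeks 40 and 64, so the natural reading is Week 40. That film stands in for one due about 40 − 28 = 12 weeks later, and Week 64 is missing.

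**The case against.** The strongest reply is that nothing essential is lost. The objective is worded in terms of adverse events, and the event is captured before the child leaves. In the illustration, the Week 24 table would show 3/30 in both arms. A reader might infer that the rule makes worsened KRN23 kidneys disappear from the nephrocalcinosis comparison. The documents do not support that: the triggering scan, the Early Termination scan and the by-arm event tables all keep them. This part of the reply stands in full.

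A reader might also infer that these children would have no Week 40 RGI-C. That is not supported either, since an Early Termination film would be taken and mapped to Week 40. SAP 8.5.2 also lists last-observation-carried-forward and multiple imputation as sensitivity analyses. The exit-film rules are not uniform: Table 2.3 footnote 27 does not say post-baseline for wrists and knees, and SAP 7.2.3 gives 3 months where the protocol gives 6.

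Three further arguments stand in part:
- The strict definition is not followed throughout, and a control child can be removed under 7.3.3. The asymmetry is therefore mandatory against discretionary, not certain exit against certain stay.
- Section 7.3.3 asks that clinically meaningful abnormalities be followed until resolution or until judged unlikely to resolve. It schedules no centrally read ultrasound for this.
- The 40-week paediatric Phase 2 data report no clinically meaningful renal ultrasound change (Protocol 5.2.3), so few children may be affected.

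None of these restores the later scheduled scans to the by-visit summary.

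**Conclusion.** The concern holds in limited form. By the protocol's definition, the mandatory rule reaches one arm and ends study participation. It can therefore remove worsened KRN23 children from later ultrasound visits and their denominators, and the by-time-point summary in SAP 8.8.7 can then favour KRN23 at equal risk.

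The size is illustrative. At 3 of 30 worsening per arm, the Week 64 gap is 3.1 to 10 points; over all the assumed counts shown it is 3.1 to 30 points. These figures rest on assumed event counts, no reversal and no removal of control children. Incidence of any post-baseline worsening is unaffected. For RGI-C the effect is an earlier film standing in at Week 40 and a missing Week 64 film. The point justifies a low-cost clarification and does not undermine the safety comparison as a whole.

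**What to change.** 1. Reconcile Protocol Sections 4, 7.3.3.1, 7.5.3.12 and 8.5.3 and SAP 5.16 on which arm or arms the mineralization rule covers. That clinical choice is the sponsor's.
2. Whatever the treatment decision, reword 7.3.3.1 so that it does not by itself end outcome follow-up. Where the family agrees, the child stays in the Week 40 and Week 64 imaging already scheduled.
3. State in the SAP how ultrasounds and radiographs taken after treatment discontinuation enter the analyses, and which film is used when both an Early Termination and a scheduled film exist.
4. Add to SAP 8.8.7 a shift from baseline to worst post-baseline grade by arm, including Early Termination scans.

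The cost is protocol and SAP wording and one table. The burden is scheduled visits and imaging, including X-rays that the protocol otherwise limits at exit, for a few children no longer on treatment.
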